#### Screening/Within 72 hours of hospital admission (Day 0)

- Informed consent
- Enrollment
- Full medical history and physical exam
- Weight
- Initial plasma laboratory evaluation including the following (obtained as research purposes if not already obtained clinically
  - Complete blood cell count with platelet count
  - o PT and aPTT
  - o Fibrinogen
  - Serum creatinine
  - Urine pregnancy screening (beta-HCG)
- Research blood specimen collection

#### Day 1 after enrollment (as inpatient)

- Interval focused interim history and physical with assessment for serious adverse events, bleeding event, and/or VTE event by inpatient medical provider
- Anti-factor Xa level
- Research blood specimen

#### Day 2 after enrollment (as inpatient)

- Interval focused interim history and physical with assessment for serious adverse events, bleeding event, and/or VTE event by inpatient medical provider
- Anti-factor Xa level (if enoxaparin dose sub- or supratherapeutic)
- Research blood specimen

#### Day 3 after enrollment (if still hospitalized)

- Interval focused interim history and physical with assessment for serious adverse events, bleeding event, and/or VTE event by inpatient medical provider
- Repeat plasma laboratory evaluation including the following (obtained as research purposes if not already obtained clinically)
  - Complete blood cell count with platelet count
  - PT and aPTT
  - Fibrinogen
  - Serum creatinine
- Research blood specimen

#### Day 7 after enrollment (if still hospitalized)

- Interval focused interim history and physical with assessment for serious adverse events, bleeding event, and/or VTE event by inpatient medical provider
- Repeat plasma laboratory evaluation including the following (obtained as research purposes if not already obtained clinically)
  - o Complete blood cell count with platelet count
  - PT and aPTT
  - Fibrinogen
  - Serum creatinine
- Research blood specimen

#### Day 14 after enrollment (if still hospitalized)

- Interval focused interim history and physical with assessment for serious adverse events, bleeding event, and/or VTE event by inpatient medical provider
- Repeat plasma laboratory evaluation including the following (obtained as research purposes if not already obtained clinically)
  - Complete blood cell count with platelet count
  - PT and aPTT
  - o Fibrinogen
  - Serum creatinine
- Research blood specimen

#### 30 days (+/- 2 days) after enrollment

Patient will be assessed for SAEs, bleeding events, and VTE events via telephone call with a study team member using a standardized screening script.

#### Off-Study Criteria:

- 1. In the investigator's opinion, it is in the participant's best interest to discontinue participation.
- 2. Study discontinuation by sponsor, IRB, or other regulatory body.
- 3. Lost to follow-up: Participants will not be deemed lost to follow-up until they have had no successful contact by the end of the 30-day visit window. Sites must document all attempts to contact the participant.

# G. Potential Scientific Problems:

Although this study involves relatively minimal intervention relative to standard care for hospitalized children with potentially severe respiratory viral infections, the main potential problems and challenges involve maintaining adequate personal protection from the exposure and transmission of SARS-CoV-2 (the cause of COVID-19 disease). Accordingly, all interactions with participants will take place as part of each site's standard of care for patients with COVID-19. Clinical assessments and the procurement of biologic specimens will be obtained concurrent with routine clinical procedures so to limit the consumption of limited personal protective equipment. In order to reduce exposure of study personnel to patients positive for SARS-CoV-2 and reduce the consumption of PPE, informed consent will be obtained in accordance with FDA regulations (21 CFR 50.27(a)) that allow each site to obtain informed consent if the appropriate technology is available or utilizing the following steps:

- 1) An unsigned consent form will be provided to the parent/legal guardian by a health care worker that has already entered the patient's room
- 2) In the event direct communication with the parent/legal guardian and patient is not feasible or safe, the investigator (or designee) will arrange a three-way call or video conference with the parent/legal/guardian and impartial witness

- 3) Each site will utilize a standard practice to ensure all patients approached in a consistent fashion including:
  - a) Identification of who is on the call
  - b) Review of the informed consent with the parent/legal guardian and response to any questions they may have
  - c) Confirmation by the witness that the patient's questions have been answered
  - d) Confirmation by the investigator that the parent/legal guardian is consenting for the patient to participate in the study

If the informed consent document is obtained in person and cannot be removed from the patient's room and included in the study records due to infection control processes, the following measures will be considered compliant with FDA regulations for informed consent:

- Attestations by the witness who participated in the call and by the investigator that the patient confirmed that they agreed to participate in the study and signed the informed consent; OR
- 2) A photograph of the informed consent document with attestation by the person entering the photograph into the study record that states how that photograph was obtained and that it is a photograph of the informed consent signed by the patient.

Other challenges stem from the multi-center nature of the study, including uniformity of data collection and anticoagulant management, and timely data entry into the EDC system. These challenges are overcome via the CCC and DCC structure and close oversight of the trial, the use of EDC system with standardized eCRFs, and the agreement of all participating centers to follow the protocol-defined enoxaparin thromboprophylaxis regimen, as being consistent with their local standard practice. These potential challenges did not materialize as substantive issues in the Kids-DOTT phase 3 multicenter trial conducted by the same investigator group.

# H. Data Analysis Plan:

The statistical analysis plan was developed by the lead trial biostatistician. Subject demographics and characteristics at study entry will be summarized with counts and percentages for categorical variables, and with means, standard deviations, medians, and interquartile ranges (IQR) as appropriate, for numeric variables. Missing data will not be imputed. Analysis of the primary endpoint will be conducted on the safety population, which includes all subjects who receive at least one dose of enoxaparin. The primary endpoint, cumulative incidence of ISTH-defined [11] clinically-relevant bleeding events during hospitalization, will be calculated with the corresponding exact (Clopper-Pearson) 90% confidence intervals (90%CIs). The precision of estimates for different cumulative incidences of clinically-relevant bleeds and corresponding 90% Cis are as follows: 0/38, 0% (0-7.6)%; 1/38, 2.6% (0-11.8%); 2/38, 5.3% (0-15.7%). The secondary endpoint, twice-daily enoxaparin dose required to achieve target anti-Xa levels, will be summarized

with medians and IQRs for all the study participants combined and by age group. Medians will be compared across age groups, if there are adequate numbers in the groups, using the Kruskal-Wallis test and a *post-hoc* Bonferroni-adjusted Mann-Whitney U test, if needed. The tertiary endpoints (as outlined in Section IV.B) will be calculated as proportions and cumulative incidences with 90%CIs, and medians with IQRs.

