# B. **Principal Aims and Hypotheses**

**Specific Aim 1:** To investigate the safety of in-hospital thromboprophylaxis with twicedaily low-dose enoxaparin thromboprophylaxis (starting dose, 0.5 m/gkg subcutaneously q12 hours, adjusted to achieve a 4 hour post-dose anti-factor Xa level of 0.20-0.49 anti-Xa U/mL) in children hospitalized with COVID-19 related-illnesses, as measured by the cumulative incidence of ISTH-defined [10] clinically-relevant bleeding (primary endpoint).

Hypothesis 1: The observed cumulative incidence of ISTH-defined clinicallyrelevant bleeding is ≤2.6% (upper limit of 90% confidence interval: ≤11.8%) among children with COVID-19 who receive in-hospital thromboprophylaxis with twicedaily low-dose enoxaparin.

**Specific Aim 2:** To determine the median twice-daily enoxaparin dose, as measured in mg/kg, required to achieve a 4 hour post-dose anti-factor Xa level of 0.20-0.49 anti-Xa U/mL in children hospitalized with COVID-19 related-illnesses, and to compare dose-requirements by age group (birth to <1 year old, 1-<6 years old, 6-<13 years old, and 13-<18 years old).

Hypothesis 2: Median dose-requirement for anti-Xa-targeted thromboprophylaxis with twice-daily enoxaparin, as measured in mg/kg, in children hospitalized with COVID-19 are associated with age, with younger age groups requiring higher doses.

**Specific Aim 3 (Exploratory):** To investigate, on an exploratory basis, the efficacy of inhospital thromboprophylaxis with twice-daily enoxaparin in children hospitalized with COVID-19, as measured by the proportion of serial D-dimer levels obtained at standardized time points that are <2 times the upper limit of normal (<2x ULN) values for age (Aim 3a; surrogate marker of efficacy), the cumulative incidence of radiologicallyconfirmed HA-VTE (Aim 3b; clinical efficacy), and the median duration of in-hospital increased respiratory support (new requirement for high-flow nasal cannula, non-invasive ventilation, and/or mechanical ventilation, relative to any at-home baseline requirement; Aims 3c, clinical efficacy).

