# E. Description of Population to be Enrolled

#### 1. Target Enrollment

The target accrual is based on the primary endpoint (safety). The safety population is defined as all patients who received at least one dose of the enoxaparin regimen. In order to achieve adequate power and precision for determination of safety in the primary analysis (see also section G, below), the target enrollment is 38 evaluable children, from among a total of 12-15 participating sites. Participants who do not received at least one dose of the enoxaparin regimen (i.e. early termination, withdrawal of consent) will be replaced. Anticipating an 85% retention rate, we will enroll up to 45 participants. Both males and females of all races and ethnic groups are eligible for this study.

Table 1. Schedule of Assessments.

Assessment	Screening (Within 72 hours of hospital admission)	Enrollm ent Day 0	Day 1	Day 2	Day 3 *	Day 7 *	Day 14 *	Day 30 (+/- 2 days)
Informed consent		Х						
Enrollment		Х						
Full H&P	Х							
Focused H&P			Х	Х	Х	Х	Х	
Weight	Х							
CBC with platelet count	Х				Х	Х	Х	
PT and aPTT 	Х				Х	Х	Х	
Fibrinogen 	Х				Х	Х	Х	
Serum creatinine	Х				Х	Х	Х	
Urine pregnancy screen 	Х							
Research blood specimen 		Х	Х	Х	Х	Х	Х	
Anti-factor Xa level 			Х	+/- X				
SAE Monitoring			Х	Х	Х	Х	Х	Х
Bleeding event (based on focused interim H&P)			Х	Х	Х	Х	Х	Х
VTE event (based on focused interim H&P, with radiological confirmation when suspected clinically)			х	х	х	х	х	х
Telephone visit 								Х

Obtained for research purposes if not already being obtained clinically.

 For participants <20kg: (1) 3ml blue top tube and (1) 4mL CPT Tube (7mL total). For participants  $\ge$ 20kg, (1) 3mL blue top tube and (2) 4mL CPT tubes (11mL total). Research blood collection is for central research lab testing of D-dimer, Clot Formation and Lysis (CloFAL) assay, IL-6, and anti-SARS-CoV-2 IgG, as well as banking plasma, DNA isolated from the buffy coat, and peripheral blood mononuclear cells (PBMCs) for future research.

 Obtained at 4 hours after 1st or 2nd dose of enoxaparin, at initial dosage (mg/kg) and any subsequent change in dosage.

Focused, scripted assessment of symptoms of potential concern for bleeding events, VTE events, and SAEs. Refer to Manual of Operations.

\* If still hospitalized.

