2.5. SAMPLE SIZE

The study enrolled 38 participants

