4.2. ANALYSIS OF THE PRIMARY OUTCOME

The primary endpoint, cumulative incidence of ISTH-defined clinically-relevant bleeding events during hospitalization, will be calculated with the corresponding exact (Clopper-Pearson) 90% confidence intervals (90%Cls)

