4.5 STUDY POWER

With a sample size of 38 patients in the safety population, the precision of estimates for various cumulative incidences of clinically-relevant bleeding (with corresponding 90% CIs) was as follows: 0/38, 0% (0-7.6%); 1/38, 2.6% (0-11.8%); 2/38, 5.3% (0-15.7%).

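### Three of the exact 90% confidence limits printed for the primary endpoint at N = 38 do not match the stated Clopper-Pearson method, and Hypothesis 1 repeats one of them

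*Protocol*

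**What the plan says.** Protocol IV.H (Data Analysis Plan) says that the primary endpoint "will be calculated with the corresponding exact (Clopper-Pearson) 90% confidence intervals (90%CIs"). SAP 4.2 names the same interval: "will be calculated with the corresponding exact (Clopper-Pearson) 90% confidence intervals".

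Protocol IV.H then gives planning figures, introduced with the words "corresponding 90% Cis are as follows". For no bleeds in 38 it prints 0% (0-7.6%). For one and two bleeds it prints "1/38, 2.6% (0-11.8%); 2/38, 5.3% (0-15.7"%). SAP 4.5 repeats all three intervals, for "With a sample size of 38 patients in the safety population".

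Hypothesis 1 in Protocol I.B states that the observed incidence "is ≤2.6% (upper limit of 90% confidence interval: ≤11.8%) among children with COVID-19" receiving the regimen. These are the two figures printed for 1/38.

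On the denominator, Protocol IV.E.1 says "the target enrollment is 38 evaluable children", and SAP 2.5 reports "The study enrolled 38 participants".

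**The concern.** A two-sided Clopper-Pearson interval has a lower limit above zero whenever at least one event is observed. The zeros printed for 1/38 and 2/38 therefore cannot come from the named method. The 11.8% also looked slightly low for one event in 38.

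These figures are the plan's statement of how precisely the primary safety endpoint will be estimated, and one of them is the upper limit in Hypothesis 1. If one bleed is seen among 38 analysed children, the planned analysis will report 0.1-11.9%. That disagrees with both sets of planning figures and with the hypothesis, and a reader comparing the report with the plan would find no explanation.

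**Working it through.** **Inputs.** The method is exact Clopper-Pearson (Protocol IV.H, SAP 4.2). The level is 90%, printed with two limits and so read as two-sided with 5% in each tail; neither document describes a one-sided bound. The denominator is n = 38 (Protocol IV.E.1 and IV.H, SAP 4.5). The counts are x = 0, 1 and 2.

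**Formulas.** The lower limit is the 5th percentile of Beta(x, n − x + 1), taken as 0 when x = 0. The upper limit is the 95th percentile of Beta(x + 1, n − x).

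**Figures that reproduce.**
- 0/38: the upper limit is 1 − 0.05^(1/38) = 0.0758, or 7.581%. The printed 0-7.6% is correct.
- 2/38: the upper limit is the 95th percentile of Beta(3, 36), which is 15.656%. The printed 15.7% is correct.

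**Figures that do not.**
- 1/38, lower: 1 − 0.95^(1/38) = 0.00135, or 0.135%. Printed as 0.
- 1/38, upper: the 95th percentile of Beta(2, 37) is 11.885%, which rounds to 11.9%. Printed as 11.8%.
- 2/38, lower: the 5th percentile of Beta(2, 37) is 0.943%. Printed as 0.

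| Bleeds | Estimate | Printed | Exact | Exact, one decimal |
|---|---|---|---|---|
| 0/38 | 0% | 0-7.6% | 0-7.581% | 0-7.6% |
| 1/38 | 2.632% | 0-11.8% | 0.135-11.885% | 0.1-11.9% |
| 2/38 | 5.263% | 0-15.7% | 0.943-15.656% | 0.9-15.7% |

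**Check from the binomial tail.** At the correct upper limit for one bleed, the probability of at most one bleed must equal 0.05.
- At p = 0.118: 0.882^38 + 38 × 0.118 × 0.882^37 = 0.0085 + 0.0431 = 0.0515. This is above 0.05, so 11.8% lies inside the exact interval and is not its limit.
- At p = 0.11885: 0.0082 + 0.0418 = 0.0500.
- For the lower limits, P(X ≥ 1) at p = 0.00135 and P(X ≥ 2) at p = 0.00943 are both 0.0500.

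**Could another calculation explain the printed set?** None of those tried gives all six limits.
- One-sided 95% upper bounds would account for the zeros, but they are 7.6%, 11.9% and 15.7%, so 11.8% would still be wrong.
- Entering the rounded 2.6% instead of the count (x = 38 × 0.026 = 0.988) gives 0.129-11.838%. Entering 5.3% (x = 2.014) gives 0.958-15.706%. That matches the printed upper limits but not the zeros.
- Truncating 11.885 would give 11.8, but 7.581 and 15.656 are printed as 7.6 and 15.7, which is rounding.
- With one bleed, n = 37 gives an upper limit of 12.2% and n = 39 gives 11.6%.
- The Wald, Wilson (with and without continuity correction), Agresti-Coull, Jeffreys, mid-P, Blaker and Sterne intervals each fail on at least one limit. Agresti-Coull, for example, gives 11.8% for 1/38 but 7.9% for 0/38.

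**Effect on width.** For one bleed the exact width is 11.885 − 0.135 = 11.75 points, against 11.8 printed. For two bleeds it is 15.656 − 0.943 = 14.71 points, against 15.7 printed.

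**The case against.** The strongest reply is that this is close to typographical. The lower limits are printed as a bare 0, and 0.135% is 0 to the nearest whole per cent, so the lower limit for one bleed may be a matter of display. That is fair for this one limit, though the upper limits beside it carry one decimal. It does not cover 0.943%, which would round to 1.

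The lower limits also play no part in a safety hypothesis that uses only the estimate and the upper limit. That stands, and it is part of why the point is minor.

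Whether one bleed in 38 misses the hypothesis depends on the reading. Taken literally, 1/38 = 2.632% already exceeds 2.6%. With both figures rounded to one decimal, as in the plan's own list, the estimate meets 2.6% and the upper limit of 11.9% does not meet 11.8%. On either reading the case fails as written. Only truncating both figures lets it pass, and truncation does not fit the other printed limits.

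A further reply is that the analysed number may not be 38. SAP 4.1.1 removes eligibility violators, undosed children and those without outcome determination. With one bleed, losing one child gives an upper limit of 12.2% and losing two gives 12.5%, larger shifts than the error itself. That is correct, and it is why the report should give the interval for the actual N. It does not make the figures printed for 38 right.

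Finally, changing a hypothesis limit after enrolment could look like loosening it. The risk is real, and a dated note giving the reason answers it.

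**Conclusion.** The concern holds and is minor. Under the stated method at N = 38, the upper limit for one bleed is understated by 0.1 point (11.8% for 11.9%), and the lower limits are understated by 0.1 point for one bleed and 0.9 point for two. Hypothesis 1 carries the wrong 11.8%.

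The conclusion rests on reading a 90% interval printed with two limits as two-sided, and on 38 as the denominator; both come from the documents. The link between Hypothesis 1 and one bleed in 38 is inferred, because both of its figures match that printed line. How the errors arose cannot be settled from the documents and does not affect the conclusion.

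The effect is confined to how the primary result is described against the plan. No test, decision rule, sample size or Table 2 pause count changes, and the exact intervals are slightly narrower than those printed.

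**What to change.** In Protocol IV.H and SAP 4.5, replace the list with: 0/38, 0% (0-7.6%); 1/38, 2.6% (0.1-11.9%); 2/38, 5.3% (0.9-15.7%).

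In Hypothesis 1, change the upper limit to 11.9% and state that the pair of figures corresponds to one bleed in 38, rounded to one decimal. Because SAP 2.5 shows that enrolment is complete, record this in a dated note as an arithmetic correction and not a change of benchmark.

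In the final report, give the exact interval for the number actually analysed, and mention the correction wherever the result is set beside the plan.

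The cost is wording only: no more patients and no change to the analysis. The drawbacks are that the hypothesis limit becomes 0.1 point less favourable and that a correction made after enrolment has to be documented.

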# I. Data Management and Security

At the Data Coordinating Center (DCC) level, data management and security are facilitated via a JHACH-hosted, web-based, secure, user-restricted, password-protected, Electronic Data Capture (EDC) system, REDCap. When combined with the Standard Operating Procedures of the COVAC-TP trial DCC at JHACH (sponsoring institution), REDCap fosters 21CFR part 11 adherence. Electronic case report form (eCRF) additions, modification of programmed data quality assurance alerts, and programming of reports within the EDC system is overseen by the DCC. Data export and transfers to the JHACH-based lead biostatistician at the DCC are executed via a secure, user-restricted, password-protected server that resides behind the firewall at the Johns Hopkins University School of Medicine.

At the participating site level, the EDC system is used by Principal Investigators (PIs) and their designees for participant enrollment, and data collection, and query resolution. Data collection in the EDC system includes protected health information (PHI), limited to date of birth and dates of events. In addition to using the EDC system, PIs at participating sites will maintain a local "COVAC-TP participant key" as a password-protected file on a secure shared drive behind the institutional firewall. This key will consist of each participant's unique study ID code (centrally generated, via the EDC system) along with his/her Medical Record Number at the local medical institution. Any hard copy records containing PHI – including the regulatory binder for the trial as well as individual participant study binders -- will be kept in a locked file cabinet under the local PI's direct oversight.

At the CCC level, administrative access to the COVAC-TP instance in the EDC system is granted to the CCC project managers on a limited basis. Specifically, this user-restricted role is used for query generation, and has "view-only" access within the eCRFs.

In addition, the Johns Hopkins All Children's Pediatric Biorepository at the CCC, serving as the central biorepository for the trial, facilitates data management and security by means of a 21 CFR part-11-adherent web-based LIMs system (STARLIMSTM, Abbot Informatics), that affords password-protected, user-restricted access to Biorepository staff only, and consists of PHI-free data on specimen/derivative inventory and pre-analytical quality assurance.

# J. Data Safety and Monitoring Plan

#### 1. DSMP Summary

An independent Data and Safety Monitoring Board (DSMB) consisting of a pediatric hematologist, a pediatric critical care or hospital medicine physician, and a PhD-level

biostatistician will be established and supported via the Pediatric Data Coordinating Center at Johns Hopkins All Children's. The DSMB will convene at least quarterly throughout the trial, including interim analyses for safety monitoring, to review confidential and de-identified data. Criteria for halting enrollment pending further evaluation by the DSMB are shown in Table 2, below. At that time, the DMSB will consider a recommendation to terminate versus continue the trial, based on evaluation of most up-to-date literature on the rate of clinically-relevant bleeding among children hospitalized with COVID-19 outside of the trial.

A Medical Safety Officer (MSO) will function for additional safety oversite for the Overall PI, and to facilitate timely sponsor-level SAE review and communication with the DSMB. The MSO will perform an independent determination of each SAE that has been locally determined by the responsible site PI, regarding relatedness to study intervention. If EITHER determination is that the SAE is "related", the SAE will be reported to the DSMB chair. Reporting timelines are provided in the Manual of Operations

